8.7. Hospitalization

Hospitalization is defined as any initial admission (even less than 24 hours) in a hospital or equivalent healthcare facility or any prolongation of an existing admission. Admission also includes transfer within the hospital to an acute/intensive care unit (eg, from the psychiatric wing to a medical floor, medical floor to a coronary care unit, or neurological floor to a tuberculosis unit). An emergency room visit does not necessarily constitute a hospitalization; however, the event leading to the emergency room visit should be assessed for medical importance.

Hospitalization does not include the following:

- Rehabilitation facilities;
- Hospice facilities;
- Respite care (eg, caregiver relief);
- Skilled nursing facilities;
- Nursing homes;
- Same-day surgeries (as outpatient/same-day/ambulatory procedures).

Hospitalization or prolongation of hospitalization in the absence of a precipitating, clinical AE is not in itself an SAE. Examples include:

- Admission for treatment of a preexisting condition not associated with the development of a new AE or with a worsening of the preexisting condition (eg, for workup of persistent pre-treatment laboratory abnormality);
- Social admission (eg, patient has no place to sleep);
- Administrative admission (eg, for yearly physical examination);
- Protocol-specified admission during a study (eg, for a procedure required by the study protocol);
- Optional admission not associated with a precipitating clinical AE (eg, for elective cosmetic surgery);
- Hospitalization for observation without a medical AE;
- Preplanned treatments or surgical procedures. These should be noted in the baseline documentation for the entire protocol and/or for the individual patient;
- Admission exclusively for the administration of blood products.

Diagnostic and therapeutic noninvasive and invasive procedures, such as surgery, should not be reported as AEs. However, the medical condition for which the procedure was performed should be reported if it meets the definition of an AE. For example, an acute appendicitis that begins during the AE reporting period should be reported as the AE and the resulting appendectomy should be recorded as treatment of the AE.

8.8. Severity Assessment

AEs will be reported using concise medical terminology (verbatim) as well as the Common Terminology Criteria (CTC) term for Adverse Events (Version 4.03, Publish Date: June 14, 2010, <http://ctep.cancer.gov/reporting/ctc.html>) listed in the Cancer Therapy Evaluation Program.

The investigator may use the following definitions of Severity in accordance with CTCAE Version 4.03 to describe the maximum intensity of the adverse event.

GRADE	Clinical Description of Severity
0	No change from normal or reference range (this grade is not included in the Version 4.03 CTCAE document but may be used in certain circumstances.)
1	MILD adverse event
2	MODERATE adverse event
3	SEVERE adverse event
4	LIFE-THREATENING consequences; urgent intervention indicated
5	DEATH RELATED TO adverse event

Note the distinction between the severity and the seriousness of an AE. A severe event is not necessarily an SAE. For example, a headache may be severe (interferes significantly with the patient's usual function) but would not be classified as serious unless it met one of the criteria for SAEs, listed above.

8.9. Causality Assessment

The investigator's assessment of causality must be provided for all AEs (serious and non-serious); the investigator must record the causal relationship in the CRF, as appropriate, and report such an assessment in accordance with the SAE reporting requirements if applicable. An investigator's causality assessment is the determination of whether there exists a reasonable possibility that the investigational product caused or contributed to an AE; generally the facts (evidence) or arguments to suggest a causal relationship should be provided. If the investigator does not know whether or not the investigational product caused the event, then the event will be handled as "related to investigational product" for reporting purposes, as defined by the sponsor (see the section on [Reporting Requirements](#)). If the investigator's causality assessment is "unknown but not related to investigational product," this should be clearly documented on study records.

In addition, if the investigator determines that an SAE is associated with study procedures, the investigator must record this causal relationship in the source documents and CRF, as appropriate, and report such an assessment in accordance with the SAE reporting requirements, if applicable.

8.10. Exposure During Pregnancy

For both unapproved/unlicensed products and for marketed products, an exposure during pregnancy occurs if:

1. A female becomes, or is found to be, pregnant either while receiving or having been exposed (eg, because of treatment or environmental exposure) to the investigational product; or the female becomes, or is found to be pregnant after discontinuing and/or being exposed to the investigational product;

An example of environmental exposure would be a case involving direct contact with a Pfizer product in a pregnant woman (eg, a nurse reports that she is pregnant and has been exposed to chemotherapeutic products).

2. A male has been exposed (eg, because of treatment or environmental exposure) to the investigational product prior to or around the time of conception and/or is exposed during his partner's pregnancy.

If a study patient or study patient's partner becomes or is found to be pregnant during the study patient's treatment with the investigational product, the investigator must submit this information to the Pfizer drug safety unit on a Serious Adverse Event (SAE) Report Form and Exposure During Pregnancy (EDP) supplemental form, regardless of whether an SAE has occurred. In addition, the investigator must submit information regarding environmental exposure to a Pfizer product in a pregnant woman (eg, a patient reports that she is pregnant and has been exposed to a cytotoxic product by inhalation or spillage) using the EDP supplemental form. This must be done irrespective of whether an AE has occurred and within 24 hours of awareness of the exposure. The information submitted should include the anticipated date of delivery (see below for information related to termination of pregnancy).

Follow-up is conducted to obtain general information on the pregnancy and its outcome for all EDP reports with an unknown outcome. The investigator will follow the pregnancy until completion (or until pregnancy termination) and notify Pfizer of the outcome as a follow-up to the initial EDP supplemental form. In the case of a live birth, the structural integrity of the neonate can be assessed at the time of birth. In the event of a termination, the reason(s) for termination should be specified and, if clinically possible, the structural integrity of the terminated fetus should be assessed by gross visual inspection (unless preprocedure test findings are conclusive for a congenital anomaly and the findings are reported).

If the outcome of the pregnancy meets the criteria for an SAE (ie, ectopic pregnancy, spontaneous abortion, intrauterine fetal demise, neonatal death, or congenital anomaly [in a live-born baby, a terminated fetus, an intrauterine fetal demise, or a neonatal death]), the investigator should follow the procedures for reporting SAEs.

Additional information about pregnancy outcomes that are reported as SAEs follows:

- Spontaneous abortion includes miscarriage and missed abortion;
- Neonatal deaths that occur within 1 month of birth should be reported, without regard to causality, as SAEs. In addition, infant deaths after 1 month should be reported as SAEs when the investigator assesses the infant death as related or possibly related to exposure to the investigational product.

Additional information regarding the exposure during pregnancy may be requested by the investigator. Further follow-up of birth outcomes will be handled on a case-by-case basis (eg, follow-up on preterm infants to identify developmental delays). In the case of paternal exposure, the investigator will provide the study patient with the Pregnant Partner Release of Information Form to deliver to his partner. The investigator must document in the source documents that the patient was given the Pregnant Partner Release of Information Form to provide to his partner.

8.11. Occupational Exposure

An occupational exposure occurs when during the performance of job duties, a person (whether a healthcare professional or otherwise) gets in unplanned direct contact with the product, which may or may not lead to the occurrence of an adverse event.

An occupational exposure is reported to the drug safety unit within 24 hours of the investigator's awareness, using the SAE Report form, regardless of whether there is an associated AE/SAE. Since the information does not pertain to a patient enrolled in the study, the information is not reported on a Case Report Form (CRF), however a copy of the completed SAE Report form is maintained in the investigator site file.

8.12. Withdrawal Due to Adverse Events

Withdrawal due to AEs should be distinguished from withdrawal due to other causes, according to the definition of AE noted earlier, and recorded on the appropriate AE CRF page. When a patient withdraws because of an SAE, the SAE must be reported in accordance with the reporting requirements defined below.

8.13. Eliciting Adverse Event Information

The investigator is to report all directly observed AEs and all AEs spontaneously reported by the study patient/legally acceptable representative. In addition, each study patient/legally acceptable representative will be questioned about AEs.

8.14. Reporting Requirements

Each AE is to be assessed to determine if it meets the criteria for SAEs. If an SAE occurs, expedited reporting will follow local and international regulations, as appropriate.

8.14.1. Serious Adverse Event Reporting Requirements

If an SAE occurs, Pfizer Safety is to be notified within 24 hours of investigator awareness of the event.

In particular, if the SAE is fatal or life-threatening, notification to Pfizer must be made immediately, irrespective of the extent of available AE information. This time frame also applies to additional new information (follow-up) on previously forwarded SAE reports as well as to the initial and follow-up reporting of exposure during pregnancy, exposure via breastfeeding and occupational exposure cases.

In the rare event that the investigator does not become aware of the occurrence of an SAE immediately (eg, if an outpatient study patient initially seeks treatment elsewhere), the investigator is to report the event within 24 hours after learning of it and document the time of his or her first awareness of the AE.

For all SAEs, the investigator is obligated to pursue and provide information to Pfizer in accordance with the time frames for reporting specified above. In addition, an investigator may be requested by Pfizer to obtain specific additional follow up information in an expedited fashion. This information collected for SAEs is more detailed than that captured on the AE CRF. In general, this will include a description of the AE in sufficient detail to allow for a complete medical assessment of the case and independent determination of possible causality. Information on other possible causes of the event, such as concomitant medications, vaccines, and/or illnesses, must be provided. In the case of a patient death, a summary of available autopsy findings must be submitted as soon as possible to Pfizer or its designated representative.

8.14.2. Non-serious Adverse Event Reporting Requirements

All AEs will be reported on the AE page(s) of the CRF. It should be noted that the form for collection of SAE information is not the same as the AE CRF. Where the same data are collected, the forms must be completed in a consistent manner. For example, the same AE term should be used on both forms. AEs should be reported using concise medical terminology on the CRFs as well as on the form for collection of SAE information.

8.14.3. Sponsor's Reporting Requirements to Regulatory Authorities

AE reporting, including suspected unexpected serious adverse reactions will be carried out in accordance with applicable local regulations.

9. DATA ANALYSIS/STATISTICAL METHODS

A detailed methodology for summary and statistical analysis of the data collected in this study will be documented in a Statistical Analysis Plan will be maintained by the Sponsor. The document may modify the plans outlined in the protocol; however, any major modifications of the primary endpoint definition and/or its analysis will also be reflected in a protocol amendment.

9.1. Sample Size Determination

9.1.1. Safety Lead-In Cohort

Approximately 10 patients will be included in the single-arm open-label Phase 1 LIC. This sample size provides at least 80% probability to observe at least one AE if the true incidence of the AE in the population is at least 15%.

9.1.2. Expansion

In the expansion phase, two cohorts of patients (MDS and AML respectively) will be enrolled, approximately 30 patients each. Based on the Bayesian decision rule (Section 3.3), a minimum of 10 and a maximum of 30 patients will be needed. For the MDS cohort, with a maximum of 30 patients, the maximum width of the exact 2-sided 95% confidence intervals (CI) for CR will be ≤ 0.374 . For the AML cohort, with a maximum of 30 patients, the maximum width of the exact 2-sided 95% CI for CR will be ≤ 0.374 .

9.2. Analysis Populations

9.2.1. Full Analysis Set (FAS)

The FAS will include all enrolled patients in the respective cohort (LIC, expansion MDS, and expansion AML cohort separately), who received at least one dose of any study treatment (glasdegib or azacitidine). This will be the primary analysis population for evaluating efficacy endpoints and patient characteristics.

9.2.2. Safety Analysis Set

The safety analysis set will include all patients who receive at least one dose of any study treatment (glasdegib or azacitidine). It will be the primary analysis population for evaluating treatment administration/compliance and safety endpoints.

9.2.3. PK Analysis Set

The PK concentration analysis set is defined as all patients who are treated and who have at least 1 value of analyte concentration of glasdegib or azacitidine available. The PK parameter analysis set is defined as all patients who are treated and who have at least 1 of the PK parameters of interest.

CCI

9.3. Efficacy Analysis

Efficacy analyses will use the FAS. They will be reported for the safety LIC, the expansion MDS cohort, and expansion AML cohort separately. All CI for binary endpoint will use the exact method, unless otherwise stated.

9.3.1. Complete Response

The proportion of patients achieving CR is the primary endpoint for the expansion cohorts. The endpoint of CR will be analyzed when the endpoint is mature in the specific expansion cohort.

A confirmation of response (peripheral blood only) is required 4 weeks after the first assessment per IWG 2006 for MDS patients. The final analyses for MDS cohorts will be performed after all patients in the expansion MDS cohort have been followed for at least 28 weeks (to allow for confirmation of response per IWG 2006). No confirmation is needed for the expansion AML cohort. The final analyses for the AML cohort will be performed after all patients in this cohort have been followed for at least 24 weeks.

The proportion and two-sided 95% CI of patients achieving CR will be provided separately for the two expansion cohorts.

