2.4. Endpoints for the Expansion

Primary Endpoint

- CR rate for MDS patients ([Appendix 2](#)) and AML patients ([Appendix 11](#)).

Secondary Endpoints

- OS;
- For MDS cohort: disease-specific efficacy measures, such as marrow CR (mCR), Partial Remission (PR), Stable Disease (SD), Partial or Complete Cytogenetic Response, and Hematologic Improvement (HI) ([Appendix 2](#));
- For AML cohort: disease-specific efficacy measures, such as CR with Incomplete Hematologic Recovery (CRi), Complete Remission with partial hematologic recovery (CRh), Morphologic Leukemia-Free State (MLFS), PR, and SD ([Appendix 11](#));
- Duration of CR;
- Time to CR;

- Adverse events and laboratory abnormalities as graded by NCI CTCAE v.4.03;
- Pharmacokinetics parameters of glasdegib;
- QTc interval.

CCI

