5.4.4. Treatment Duration

Since responses to azacitidine may require 4-6 cycles of administration to emerge, treatment with the study drug combination should be continued for at least 6 cycles, or until death, unacceptable toxicity, or patient refusal whichever occurs first. If documentation of disease progression occurs within the first 6 cycles of study treatment the patient **SHOULD NOT** be withdrawn from study treatment if, in the Investigator's judgment, the patient is still likely to receive clinical benefit. In the safety LIC, patients with >30% BM blasts OR a rapidly progressive increase in the proportion of BM blasts at any point during the trial, must discontinue the study drug combination and enter follow-up.

Treatment with the study drug combination should be continued beyond 6 cycles of treatment until objective disease progression or relapse, death, unacceptable toxicity, or patient refusal whichever occurs first. Treatment should also be continued beyond 6 cycles if patients demonstrate reasonable evidence of clinical benefit, defined as HI or better in patients enrolled into the safety LIC, SD + HI or better in MDS patients enrolled to the expansion, and not meeting the criteria for disease progression for AML patients enrolled into the expansion.

If glasdegib is permanently discontinued for reasons other than objective disease progression, patient refusal, or consent withdrawal, single-agent treatment with azacitidine may be continued if, in the Investigator's judgment, a clinical benefit has been observed and following discussion between the Investigator and Sponsor.

In cases of unacceptable toxicity or pregnancy, the patient must be withdrawn from study drug combination and entered into the follow-up phase of the study.

When study treatment with both drugs (glasdegib and azacitidine) is permanently discontinued, patients will enter into the follow-up phase.

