Proposed modified IWG Myelodysplasia Response Criteria for Hematologic Improvement (HI)**

[figure not shown]
Erythroid response (pre-treatment <11g/dL)*	Hgb increase by ≥ 1.5 g/dL Relevant reduction of units of RBC transfusions by an absolute number of at least 4 RBC transfusions/8 weeks as compared to the pretreatment transfusion number in the previous 8 weeks (only RBC transfusions given for Hb ≤ 9 g/dL pretreatment will count in the RBC transfusion evaluation).
Platelet Response (pretreatment <100 x10 ⁹ /L)*	Absolute increase of ≥ 30 x10 ⁹ /L if starting with >20 x 10 ⁹ /L platelets Increase from <20 x 10 ⁹ /L to >20 x10 ⁹ /L and by at least 100%
Neutrophil Response (pretreatment <1 x 10 ⁹ /L)*	At least a 100% increase and an absolute increase >0.5 x10 ⁹ /L
Progression or relapse after HI in the absence of another explanation	At least one of the following: 
 • At least 50% decrease from maximum response levels in granulocytes or platelets; • Reduction in Hgb by ≥ 1.5g/dL; • Transfusion dependence.

*Pretreatment counts averages of at least 2 measurements (not influenced by transfusions) ≥ 1 week apart.

** Hematologic Improvement must last ≥ 8 weeks and is derived based on lab data entered in the database.

***This criteria will be applied to MDS patients enrolled in the Safety Lead-In and Expansion components of the study and patients with oligoblastic AML and CMML without proliferative disorder enrolled into the Safety Lead-In component of the study.

Appendix 3. Myelodysplastic Syndromes: 2014 Update on Diagnosis, Risk-Stratification, and Management*

* Applies to MDS patients enrolled in the Safety Lead-In and Expansion components of the study and patients with AML with 20-30% blasts and multi-lineage dysplasia and CMML without proliferative disorder enrolled into the Safety Lead-In component of the study.

Source: Schanz J, Tüchler H, et al. New comprehensive cytogenetic scoring system for primary myelodysplastic syndromes (MDS) and oligoblastic acute myeloid leukemia after MDS derived from an international database merge. J Clin Onc 2012; 30:820-29.

Figure from Garcia-Manero G. Myelodysplastic syndromes: 2014 update on diagnosis, risk stratification, and management. American Journal of Hematology 2014; 89(1):97-108.

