7.2. Efficacy Analysis

For primary and secondary efficacy analyses, no values will be imputed for missing data. Censoring for time-to-event endpoints are defined in [Section 6.1](#). In the assessment of response (at interim or final analysis), patients who are not known to have achieved response will be counted as non-responders.

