8.2.2.2.2. Other Efficacy Measures

Specifically, for AML cohort, the following binary efficacy endpoints (with 95% exact CI) will be summarized in frequency tables, proportion of patients achieving CR, CRh, CRi, CR/CRi, MLFS, PR, SD, CRc, , CRm, and CR+PR.

For MDS cohort, the following binary efficacy endpoints (with 95% exact CI) will be summarized in frequency tables, proportion of patients achieving CR, marrow CR, PR, SD, CR+PR, and Partial or Complete Cytogenetic Response, as well as the proportion of patients ever achieving HI.

The FAS will be used.

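### At the 28-week MDS analysis, hematologic improvement starting after week 20 in the last-enrolled patients cannot yet meet its 8-week rule, so the HI rate may be read slightly low

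*Protocol*

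**What the plan says.** - **Trigger.** Protocol 9.3.1 runs the MDS final analyses once every expansion MDS patient has been "followed for at least 28 weeks (to allow for confirmation of response per IWG 2006"). SAP sections 3 and 8.2.1 repeat this.
- **Reason given.** "A confirmation of response (peripheral blood only) is required 4 weeks after the first assessment per IWG 2006 for MDS patients". For AML, where no confirmation is needed, "The final analyses for the AML cohort will be performed after all patients in this cohort have been followed for at least 24 weeks".
- **HI is a secondary endpoint of the MDS cohort.** Protocol 2.4 lists "Partial or Complete Cytogenetic Response, and Hematologic Improvement (HI") among the disease-specific measures.
- **HI has a longer duration rule.** Protocol Appendix 2, and the same footnote in SAP Appendix 2: "Hematologic Improvement must last ≥ 8 weeks and is derived based on lab data entered in the database".
- **How HI is reported.** SAP 8.2.2.2.2 tabulates the MDS response rates in the full analysis set, "as well as the proportion of patients ever achieving HI".
- **Scoring.** SAP 7.2 imputes nothing, and "patients who are not known to have achieved response will be counted as non-responders". SAP 6.1.2 places HI among the response-related endpoints, so this rule reaches it.
- **Later analyses.** Protocol 9.3.3 plans an update at study conclusion for OS. The visible text plans none for HI, and protocol 9.3.6, which covers HI, sets no date.
- **Expected timing of response.** Protocol 5.4.4: "Since responses to azacitidine may require 4-6 cycles of administration to emerge".

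**The concern.** The follow-up floor was sized to the 4-week CR rule, but the same data cut also serves an endpoint whose rule is twice as long. For the last patients enrolled, the onset window is therefore four weeks shorter for HI than for CR, and the missing weeks (20 to 24) lie inside the period in which the protocol says responses may still be emerging. An improvement in progress at the cut is scored as a failure because of the calendar, and the error can only go downward.

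HI carries some weight in this protocol. Section 1.2.3 notes that patients in the AZA-001 trial with HI but no complete or partial response still had a survival benefit, and section 1.2.16.1 cites azacitidine HI rates of 44% and 49%. Readers may set the study's HI rate beside such figures.

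**Working it through.** **Inputs.** MDS floor 28 weeks; AML floor 24 weeks; CR confirmation 4 weeks (protocol 9.3.1). HI duration at least 8 weeks (Appendix 2). Cycles of 28 days, with scheduled hematology on Day 1 only from Cycle 2 and a window of -3/+14 days (Table 3). Cohort size 30 (protocol 9.1.2).

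**1. The plan's own figure.** 24 + 4 = 28 weeks. This matches, but the sum is inferred from the AML date; the documents do not write it out.

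**2. Latest qualifying onset at exactly 28 weeks.** CR: 28 - 4 = week 24. HI: 28 - 8 = week 20.

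**3. On the nominal visit grid.**

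| First seen at | Week | CR confirmed by week 28? | HI lasts 8 weeks by week 28? | HI lasts 8 weeks by week 32? |
|---|---|---|---|---|
| C5D1 | 16 | yes | yes | yes |
| C6D1 | 20 | yes | yes | yes |
| C7D1 | 24 | yes | no | yes |

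Giving HI the same 24-week onset window as CR needs 24 + 8 = 32 weeks.

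**4. Who is affected.** A patient enrolled *t* weeks before the last one has a latest qualifying onset of week 20 + *t*. For *t* of 4 or more, the window is at least 24 weeks. Only patients enrolled in about the last 4 weeks of accrual fall short.

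**5. Weight of one patient.** 1/30 = 3.3 points. For example, 15/30 = 50.0% (exact 95% CI 31.3% to 68.7%) becomes 14/30 = 46.7% (28.3% to 65.7%).

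**6. Expected loss.** The documents give neither accrual time nor HI onset times, so everything here is assumption. Take uniform accrual over *A* weeks and about 15 true HIs in 30 (close to the cited 49%). The share of patients with under 32 weeks at the cut is 4/*A*. Expected HIs missed = 15 × (share of onsets first seen at C7D1) × 4/*A*.

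| *A* (weeks) | 4/*A* | One third of onsets at C7D1 | One fifteenth at C7D1 |
|---|---|---|---|
| 13 | 31% | 1.5 patients | 0.3 |
| 26 | 15% | 0.8 | 0.15 |
| 40 | 10% | 0.5 | 0.1 |
| 52 | 8% | 0.4 | 0.08 |

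The third column puts every onset at C5D1, C6D1 or C7D1 with equal chance. The fourth puts only 20% of onsets after Day 100, spread evenly over those three visits (0.20/3 = 0.067).

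A separate bound: with 1 to 5 patients enrolled in the last 4 weeks, and 5% to 15% of patients having a first HI in weeks 20 to 24, at most 1 × 0.05 = 0.05 to 5 × 0.15 = 0.75 patients are missed, or 0.2 to 2.5 points of 30.

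**The case against.** - **28 weeks is a floor.** The text requires at least 28 weeks for all patients. On nominal visits, a cut four weeks later removes the shortfall. This stands, and it limits the point to a cut at or soon after the floor. Nothing in the plan requires a later cut.
- **The timing sentence belongs to CR.** It appears in protocol 9.3.1, section 9.3.6 sets no date for HI, and section 7.7.1 measures response through the end of treatment, so a later HI report would be consistent with the protocol. That is fair, but SAP section 3 sets a single MDS final analysis and makes no exception for HI.
- **A later HI analysis may exist.** Its absence is inferred from the visible text, and redacted blocks follow the HI paragraph. The claim has to be limited to what can be read.
- **Late onset may be rare.** The 4-to-6-cycle statement explains why treatment continues; it is not an onset distribution. In the lead-in cohort, 4 of 5 responses came by Day 100, before C5D1. Those were CR and marrow CR in a small mixed cohort, so they guide rather than settle the matter, but they make the one-third share at C7D1 look high.
- **The visit window.** A C9D1 visit at the end of its +14-day window falls at week 34. It would be wrong to count every patient with under 34 weeks as affected, since that assumes the full window is always used.
- **Any fixed cut misses some later onsets.** This is true of an ever-achieved endpoint. The point here is narrower: HI does not get the onset window that the plan gives CR.
- **Nothing formal depends on HI.** SAP 4.1 states no hypotheses, and the futility rule uses CR alone. This stands and keeps the severity low.

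**Conclusion.** The mismatch is real and minor. If data are cut when the last MDS patient reaches 28 weeks, an HI that began after week 20 cannot yet qualify in that patient and counts as non-response. On nominal visits this is confined to patients enrolled in about the last 4 weeks of accrual. The bias is downward: 3.3 points per missed patient, with an expected loss between well under one patient and about 1.5. The upper figure needs both 13-week accrual and one third of onsets at C7D1, and the documents support neither assumption. The exact 95% interval at n = 30 is up to 37 points wide.

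A reader might infer that late improvements are lost across the whole cohort, or that a tenth of true HIs will be missed. The documents do not support either: patients enrolled earlier have longer follow-up, and the one-tenth figure (1.5 of 15) is only the worst case in the table. Nor does the point touch the primary CR rate, the futility rule or OS.

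**What to change.** In protocol 9.3.6 and SAP sections 3 and 8.2.2.2.2, add one sentence choosing either option:

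- the definitive MDS HI rate is analysed when every patient has at least 32 weeks of follow-up, plus the visit window (32 + 2 = 34 weeks to cover +14 days), or has ended treatment; or
- the definitive HI rate is reported with the study-end update already planned for OS.

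Leave the CR analysis date unchanged. An HI rate shown at the CR analysis should be labelled preliminary, with a note that for the last-enrolled patients it covers onsets only to about week 20.

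The cost is small. Treatment and per-cycle hematology continue past the cut, so no new visits or data are needed. The downside is that the final HI table comes later than the CR result, by several weeks or at study end.
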